In the following situations where two visits are close to each other, only one visit should take place:

- If V40A is more than 10 weeks after randomisation and before the planned V26, only V40A should be performed
- If V26 and FU2 visit windows overlap according to visit schedule, only V26 should be performed
- If V40 and FU1 visit windows overlap according to visit schedule, only V40 should be performed
- If V40 and FU2 visit windows overlap according to visit schedule, only V40 should be performed

Diary records after premature discontinuation of trial product:

The Subject will be handed out premature discontinuation diaries to fill in:

- Date, actual clock time and value of the SMPG measurements performed as part of the 8-point profiles on the two consecutive days just before Visit 26 and Visit 40
- Hypoglycaemic episodes. The following information should be recorded:

- Start date and time of hypoglycaemic episode
- Time and value of plasma glucose level before treating the episode (if available) and any follow up measurements.
- Whether the episode was symptomatic (Yes/No)

A hypoglycaemic episode starting without symptoms should be updated to symptomatic if the Subject experience symptoms later during the episode.

- Was the hypoglycaemic episode associated with severe neuroglycopenia, usually resulting in coma or seizure and requiring parenteral therapy (glucagon or intravenous glucose)³⁴? (Layman language used in the Subject diaries: Was the low blood glucose episode associated with symptoms severe enough to result in unconsciousness or a seizure and was glucagon (an injection) or IV glucose/sugar (drip) needed for your child to recover?)
- Hyperglycaemic episodes (see section [8.5.1.2](#))

Hypoglycaemic and/or hyperglycaemic episode must be reported in the diary until Visit 40 has been completed.

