1.2 Scope of the statistical analysis plan

This statistical analysis plan (SAP) is based on the protocol *Efficacy and Safety of Faster-acting insulin aspart compared to NovoRapid® both in Combination with Insulin Degludec in Children and Adolescents with Type 1 Diabetes*, version 5.0 (dated 16 January 2017). The statistical analyses and derivations of endpoints presented in this SAP are almost identical to those described in the protocol. It contains minor clarifications for derivations, calculation of endpoints and analyses as well as a few additions.

The changes to the statistical considerations proposed in this SAP and the reasons for the changes are described in section [3](#) and will be reported in the clinical trial report (CTR).

2 Statistical considerations

General considerations

In general, for endpoints evaluated as a change from baseline and/or where a baseline adjustment is made, baseline is defined as information collected at the randomisation visit (Visit 14). In case a measurement is not available at the randomisation visit, the most recent measurement prior to the randomisation visit will be used as baseline.

Two observation periods are defined, “in trial” and “on treatment”, and it will be specified which period each analysis will use.

- In trial: the observation period from date of randomisation and until last trial -related Subject-site contact. The in trial observation period includes data collected after treatment discontinuation.
- On treatment: the observation period from date of first dose of randomised NovoRapid®/fast-acting insulin aspart and no later than 7 days after the day of last dose of NovoRapid®/fast-acting insulin aspart. The on treatment observation period includes data collected up to and including 7 days after treatment discontinuation.

All primary and secondary efficacy endpoints will be summarised and analysed using the full analysis set (FAS), unless otherwise stated. Safety endpoints will be summarised using the safety analysis set (SAS) and analysed using the FAS, unless otherwise stated.

Presentation of results from a statistical analysis will include the estimated mean treatment effects (LSMeans) for change from baseline, if applicable. Estimated mean treatment differences (or ratios) will be presented together with two-sided 95% confidence intervals for all endpoints analysed statistically.

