2.4.1.1 Efficacy endpoints

All endpoints except insulin dose in this section will be assessed using the FAS and the in trial observation period and repeated using the on treatment observation period. Insulin dose will only be presented using the on treatment observation period.

The following endpoints will be assessed 26 weeks after randomisation:

Change from baseline in 8-point profiles.

PPG increments based on the 8-point profiles will be derived separately for plasma glucose (PG) measurements made 1 hour after the meal. In the following section this distinction will be considered implicit and without further explanation. PPG will be recorded by the Subject as part of two 8-point profiles prior to the visits. PPG increment for each meal (breakfast, lunch, main evening meal) will be derived from the 8-point profile as the difference between PPG values and the PG value before meal in each separate profile. The mean of the derived increments will then be calculated separately for each meal. Mean PPG increment over all meals will be derived as the mean of all corresponding mean meal increments.

- Change from baseline in mean PPG and PPG increment over all three meals

Mean PPG and PPG increment will be analysed separately using a model similar to 1), except with the corresponding baseline value as covariate.

- Change from baseline in individual meal (breakfast, lunch and main evening meal)
PPG and PPG increment from 8-point profile

PPG and PPG increment endpoints for the individual meals (breakfast, lunch, main evening meal) will be analysed separately using a model similar to 1) except with the corresponding baseline value as covariate.

- Change from baseline in mean of the 8-point profile

The mean of the 8-point profile is defined as the area under the profile divided by the measurement time, and is calculated using the trapezoidal method. Mean of the 8-point profile will be analysed using a model similar to 1) except with the corresponding baseline value as covariate.

- Fluctuation in 8-point profile

The fluctuation in the 8-point profile is defined as

$$\frac{1}{T} \int_0^T |PG(t) - \bar{PG}| dt,$$

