where T , $PG(t)$ and \bar{PG} denotes the length of the profile, the PG value at time t and the mean of the profile, respectively. Fluctuation in the 8-point profile will be logarithmically transformed and analysed in the same way as mean of the profile is analysed except with the corresponding log-transformed baseline values as covariate. Estimated treatment means and the estimated treatment difference with corresponding 95% CI will be back-transformed to the original scale, resulting in estimated geometric means, a treatment ratio and a 95% CI for the treatment ratio.

- Change from baseline in FPG

Change from baseline in FPG will be analysed using a model similar to 1) except with baseline FPG as covariate.

- Change from baseline in 1,5-anhydroglucitol

Change from baseline in 1,5-anhydroglucitol will be using a model similar to 1) except with baseline 1,5-anhydroglucitol as covariate.

- Percentage of Subjects reaching HbA_{1c} target (HbA_{1c} < 7.5%) according to ISPAD guidelines³

This dichotomous (responder/non-responder) endpoint will be defined based on whether a Subject has met the ISPAD HbA_{1c} target (HbA_{1c} < 7.5%) 26 weeks after randomisation.

This responder endpoint will be analysed based on a logistic regression model using treatment, region and strata as factors, and baseline HbA_{1c} as covariate. In the in trial

observation period analysis, Subjects withdrawn from trial are included as non-responders. In the on treatment observation period analysis, both Subjects who prematurely discontinue fast-acting insulin aspart/NovoRapid® or withdraw from trial are included as non-responders. Subjects without HbA_{1c} at week 26 will be treated as non-responders for both the in trial and on treatment observation period analyses.

- Percentage of Subjects reaching HbA_{1c} target (HbA_{1c} < 7.5%) according to ISPAD guidelines, without severe hypoglycaemia³.
This dichotomous (responder/non-responder) endpoint will be defined based on whether a Subject has met the ISPAD HbA_{1c} target (HbA_{1c} < 7.5%) 26 weeks after randomisation without treatment emergent severe hypoglycaemic episodes³.

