2.4.1.2 Safety endpoints

All safety endpoints will be compared using the on treatment observation period. In terms of adverse events, as a minimum, serious adverse events will be tabulated separately also using the in trial observation period.

All events in the in trial observation period will be listed with information about whether it appeared in the on treatment observation period or not.

Classification of Hypoglycaemia:

Treatment emergent: hypoglycaemic episodes will be defined as treatment emergent if the onset of the episode occurs on or after the first day of treatment with investigational medicinal product (IMP) after randomisation, and no later than 1 day after the last day on IMP.

Nocturnal hypoglycaemic episodes: are episodes occurring between 23:00 and 07.00 both inclusive.

[figure not shown]
Hypoglycaemic episodes are classified according to ISPAD's definition of severe hypoglycaemia⁴, as well as Novo Nordisk classification of hypoglycaemia (see [Figure 2-1](#)) and the ADA classification of hypoglycaemia⁵ (see [Figure 2-2](#)).

Novo Nordisk classification of hypoglycaemia in paediatrics

In normal physiology, symptoms of hypoglycaemia occur below a PG level of 3.1 mmol/L (56 mg/dL)⁶. Therefore, Novo Nordisk has included hypoglycaemia with PG levels below this cut-off point in the definition of blood glucose (BG) confirmed hypoglycaemia.

Novo Nordisk uses the following classification (see [Figure 2–1](#)) in addition to the ADA classification:

- Severe hypoglycaemia according to the ISPAD classification⁴: Was the hypoglycaemic episode associated with severe neuroglycopenia, usually resulting in coma or seizure and requiring parenteral therapy (glucagon or intravenous glucose)?
- Symptomatic BG confirmed hypoglycaemia: An episode that is BG confirmed by PG value $< 3.1 \text{ mmol/L (56 mg/dL)}$ **with** symptoms consistent with hypoglycaemia.
- Asymptomatic BG confirmed hypoglycaemia: An episode that is BG confirmed by PG value $< 3.1 \text{ mmol/L (56 mg/dL)}$ **without** symptoms consistent with hypoglycaemia.
- Severe or BG confirmed symptomatic hypoglycaemia: An episode that is severe according to the ISPAD classification⁴ or BG confirmed by a PG value $< 3.1 \text{ mmol/L (56 mg/dL)}$ **with** symptoms consistent with hypoglycaemia.
- BG confirmed hypoglycaemia: An episode that is BG confirmed by a PG value $< 3.1 \text{ mmol/L (56 mg/dL)}$ **with or without** symptoms consistent with hypoglycaemia.

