Data on treatment emergent hypoglycaemic episodes are presented in terms of the number of Subjects with at least one event (N), the percentage of Subjects with at least one event (%), the number of events (E) and the event rate per 100 years of exposure (R). Separate summaries are made by severity (the ISPAD criterion for severe hypoglycaemia⁴) considering all episodes, nocturnal and daytime episodes using Novo Nordisk and ADA classified episodes. Episodes will also be summarised overall and by category in relation to time since start of meal, as occurring within the following time intervals:

- During first 1, 2, and 4 hours after start of meal
- Between 1 (exclusive) to 2 hours (inclusive) after start of meal
- Between 2 (exclusive) to 3 hours (inclusive) after start of meal
- Between 3 (exclusive) to 4 hours (inclusive) after start of meal
- Between 2 hours (exclusive) to 4 hours (inclusive) after start of meal

Non-treatment emergent hypoglycaemic episodes will be listed.

The number of treatment emergent severe or BG confirmed hypoglycaemic episodes (all, daytime, nocturnal) will be analysed using a negative binomial regression model with a log-link function and the logarithm of the time period for which a hypoglycaemic episode is considered treatment emergent as offset. The model will include treatment, region and strata as factors, and will be based on the FAS. To the extent where data allow, separate analyses will be performed for severe episodes (all).

- Number of treatment emergent adverse events (AEs)

AEs will be coded using the Medical Dictionary for Regulatory Activities (MedDRA). AEs will be presented based on system organ class and preferred terms.

A Treatment Emergent Adverse Event (TEAE) is defined as an event that has an onset date on or after the first day of exposure to randomised treatment, and no later than 7 days after the last day of randomised treatment.

TEAEs are summarised descriptively, whereas AE's not defined as treatment emergent are presented in listings, including AEs reported in the 30-day follow-up period. The summaries of TEAEs are made displaying the number of Subjects with at least one event, the percentage of Subjects with at least one event, the number of events and the event rate per 100 Subjects years of exposure. These summaries are done by seriousness, severity, relation to insulin treatment, relation to device, withdrawal due to AEs and outcome.

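### The in-trial analysis of HbA1c below 7.5% without severe hypoglycaemia can count as a responder a subject who had a severe episode after stopping trial product

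*SAP*

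**What the plan says.** - **Two analyses.** SAP 2.4.1.1 states that the efficacy endpoints other than insulin dose "will be assessed using the FAS and the in trial observation period and repeated using the on treatment observation period".
- **The two periods.** From the general considerations in SAP section 2: "The in trial observation period includes data collected after treatment discontinuation"; "The on treatment observation period includes data collected up to and including 7 days after treatment discontinuation".
- **The endpoint.** A responder has HbA1c below 7.5% "26 weeks after randomisation without treatment emergent severe hypoglycaemic episodes" (SAP 2.4.1.1). The same definition serves both analyses.
- **The window.** Under SAP 2.4.1.2 a hypoglycaemic episode is treatment emergent if it starts on or after the first day of randomised product and "no later than 1 day after the last day on IMP".
- **Non-responder rules.** In trial: withdrawal from the trial, or no week 26 HbA1c. On treatment: those two, plus stopping the randomised bolus insulin early (SAP 2.4.1.1).
- **Data collection.** Under protocol 8.2, subjects who stop product keep Visits 26 and 40 and receive a diary that includes the severe-episode question. "Hypoglycaemic and/or hyperglycaemic episode must be reported in the diary until Visit 40 has been completed".
- **Use of later episodes.** From SAP 2.4.1.2: "All safety endpoints will be compared using the on treatment observation period"; "Non-treatment emergent hypoglycaemic episodes will be listed". The same section lists every in-trial event with an on-treatment flag and adds an in-trial table of serious adverse events.

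Protocol 17.4.1.1 and 17.4.1.2 carry the same definition and the same window, so neither document resolves the point for the other.

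**The concern.** The endpoint has two parts, and in the in-trial version they cover different follow-up. The HbA1c part runs to week 26 whether or not the subject is still on product. The hypoglycaemia part ends 1 day after the last dose. For a subject who stops early and stays in the trial, most of the 26 weeks may count for HbA1c and not for hypoglycaemia.

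The resulting error goes one way: it can only add responders. It also arises only through stopping product, which could differ between arms because the post-meal arm is open-label. At stake is whether the in-trial percentage means what its name says. The information needed to get it right is already collected.

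**Working it through.** **Step 1. Trace the rules.** The plan gives no expected rate or power for this endpoint, so there is no figure to reproduce. The check is whether the definitions allow the misclassification.

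| Situation | In-trial version | On-treatment version |
|---|---|---|
| Withdrew, or no week 26 HbA1c | non-responder | non-responder |
| Stopped product, stayed in trial | not in itself a failure | non-responder |
| Severe episodes that count | up to 1 day after last product day | up to 1 day after last product day |
| Stopped, later severe episode, HbA1c below 7.5% at Visit 40 | **responder** | non-responder |

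Example: a subject stops at week 4, attends Visits 26 and 40, has a severe episode at week 15 and is below 7.5% at Visit 40. The HbA1c condition is met. The week 15 episode falls outside the window, so it does not disqualify. There was no withdrawal and no missing HbA1c. The in-trial analysis records a responder without severe hypoglycaemia.

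**Step 2. Bound the number at risk.** SAP 2.1 gives 250 subjects per arm and expects fewer than 10% to stop product: 250 × 0.10 = 25 per arm as the upper limit.

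**Step 3. Estimate how many would be reclassified.** Three inputs are assumptions, because the documents do not give them:

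- severe-episode rate off product, r: 1 to 20 per 100 subject-years
- mean time off product, w: 6.5 to 25.7 weeks
- share of these subjects below 7.5% at week 26, q: 30% to 60%

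Risk of at least one severe episode: p = 1 − exp(−(r/100) × w/52.18). Reclassified subjects per arm: m = 25 × p × q. Percentage points: 100 × m/250.

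| r | w (weeks) | q | p | m per arm | Percentage points |
|---|---|---|---|---|---|
| 1 | 6.5 | 0.30 | 0.0012 | 0.009 | 0.004 |
| 5 | 13 | 0.60 | 0.0124 | 0.19 | 0.07 |
| 20 | 13 | 0.60 | 0.0486 | 0.73 | 0.29 |
| 20 | 25.7 | 0.60 | 0.0938 | 1.41 | 0.56 |

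**Step 4. Two variations.** SAP 2.1 also expects up to 5% to withdraw from the trial, and those subjects are non-responders already. If they are all among the stoppers (assumption), 250 × (0.10 − 0.05) = 12.5 per arm remain at risk, and the last row falls to 0.70 subjects (0.28 points). In the other direction, a rate of 50 per 100 subject-years, outside the assumed range, would turn the last row into 3.3 subjects (1.3 points). The ceiling therefore depends on the assumed rate.

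**The case against.** The best case for the plan is that comparing hypoglycaemia on treatment is an explicit choice, stated in both documents. After stopping, subjects move to marketed insulin chosen by the investigator, so an episode weeks later arises on another regimen. The endpoint is supportive, lies outside the three-step test sequence and is not one of the starred key endpoints. The on-treatment repeat already gives a stricter version.

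Much of this stands. It justifies the on-treatment safety comparison and keeps the point minor. It does not explain the in-trial composite. HbA1c after stopping also reflects another regimen, yet that version counts it. The SAP gives the two versions different non-responder rules, but nowhere says that the hypoglycaemia part of the in-trial version is deliberately limited to exposure.

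A reader might infer three stronger things, which the documents do not support:

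- *That episodes after stopping go unused.* They enter no hypoglycaemia summary or model, but they are listed. Those meeting the serious criteria also need an adverse event form (protocol 8.5.1.1) and so reach the in-trial table. Protocol 12.1.2 names convulsions among its examples of important medical events, so a seizure would probably qualify, subject to medical judgement. That table does not correct the responder count.
- *That the hypoglycaemia comparison loses a different share of subjects in each arm.* The negative binomial model uses the full analysis set with log treatment-emergent time as offset. Subjects who stop remain in it with their time on product; only off-product time is left out. Informative stopping is possible, but that is a different and weaker claim.
- *That the model for severe or BG confirmed episodes should be rerun in trial.* Contacts are weekly on product, with 4-point profiles on the three days before each. After stopping they fall to a few visits and at least one call for earlier stoppers, and 4-point profiles no longer apply at Visits 26 and 40 (protocol 8.2 and amendment 2). BG confirmed episodes include asymptomatic low readings, so detection depends on how often glucose is measured. Pooling the two periods would mix unequal ascertainment. Severe episodes are defined by clinical severity rather than by a reading, so they are less exposed to this problem.

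**Conclusion.** The point stands, and it is narrow. The definitions alone show that the in-trial version can label as free of severe hypoglycaemia a subject who had a severe episode more than 1 day after stopping product. The on-treatment version cannot.

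The expected effect is about 0 to 1.4 subjects per arm, at most about 0.6 percentage points. This rests on the plan's limit of 10% stopping and on assumed values for the severe rate, the time off product and the share at target. No confirmatory conclusion changes. The reason to act is that the label is wrong for these subjects and the correction uses data already collected.

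**What to change.** Add one sentence to the endpoint's definition in SAP 2.4.1.1: in the in-trial analysis, any severe hypoglycaemic episode from randomisation to the week 26 visit makes the subject a non-responder, while the on-treatment analysis keeps the treatment-emergent definition. If limiting that part to exposure is intended, the SAP should say so and label the in-trial result accordingly.

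Optionally, add a descriptive in-trial count of severe episodes by arm. No in-trial model for BG confirmed episodes is needed.

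The cost is one SAP sentence and no new data collection. The in-trial responder percentage may become slightly lower.

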2.4.1.2 Safety endpoints

All safety endpoints will be compared using the on treatment observation period. In terms of adverse events, as a minimum, serious adverse events will be tabulated separately also using the in trial observation period.

All events in the in trial observation period will be listed with information about whether it appeared in the on treatment observation period or not.

Classification of Hypoglycaemia:

Treatment emergent: hypoglycaemic episodes will be defined as treatment emergent if the onset of the episode occurs on or after the first day of treatment with investigational medicinal product (IMP) after randomisation, and no later than 1 day after the last day on IMP.

Nocturnal hypoglycaemic episodes: are episodes occurring between 23:00 and 07.00 both inclusive.

[figure not shown]
Hypoglycaemic episodes are classified according to ISPAD's definition of severe hypoglycaemia⁴, as well as Novo Nordisk classification of hypoglycaemia (see [Figure 2-1](#)) and the ADA classification of hypoglycaemia⁵ (see [Figure 2-2](#)).

Novo Nordisk classification of hypoglycaemia in paediatrics

In normal physiology, symptoms of hypoglycaemia occur below a PG level of 3.1 mmol/L (56 mg/dL)⁶. Therefore, Novo Nordisk has included hypoglycaemia with PG levels below this cut-off point in the definition of blood glucose (BG) confirmed hypoglycaemia.

Novo Nordisk uses the following classification (see [Figure 2–1](#)) in addition to the ADA classification:

- Severe hypoglycaemia according to the ISPAD classification⁴: Was the hypoglycaemic episode associated with severe neuroglycopenia, usually resulting in coma or seizure and requiring parenteral therapy (glucagon or intravenous glucose)?
- Symptomatic BG confirmed hypoglycaemia: An episode that is BG confirmed by PG value $< 3.1 \text{ mmol/L (56 mg/dL)}$ **with** symptoms consistent with hypoglycaemia.
- Asymptomatic BG confirmed hypoglycaemia: An episode that is BG confirmed by PG value $< 3.1 \text{ mmol/L (56 mg/dL)}$ **without** symptoms consistent with hypoglycaemia.
- Severe or BG confirmed symptomatic hypoglycaemia: An episode that is severe according to the ISPAD classification⁴ or BG confirmed by a PG value $< 3.1 \text{ mmol/L (56 mg/dL)}$ **with** symptoms consistent with hypoglycaemia.
- BG confirmed hypoglycaemia: An episode that is BG confirmed by a PG value $< 3.1 \text{ mmol/L (56 mg/dL)}$ **with or without** symptoms consistent with hypoglycaemia.
- Severe or BG confirmed hypoglycaemia: An episode that is severe according to the ISPAD classification⁴ or BG confirmed by a PG value $< 3.1 \text{ mmol/L (56 mg/dL)}$ **with or without** symptoms consistent with hypoglycaemia.

[figure not shown]

Note: Glucose measurements are performed with capillary blood calibrated to plasma equivalent glucose values

Figure 2–1 Novo Nordisk classification of hypoglycaemia in paediatrics

ADA⁵/ISPAD classification of hypoglycaemia in paediatrics

- Severe hypoglycaemia according to the ISPAD classification⁴: Was the hypoglycaemic episode associated with severe neuroglycopenia, usually resulting in coma or seizure and requiring parenteral therapy (glucagon or intravenous glucose)?
- Asymptomatic hypoglycaemia: An episode not accompanied by typical symptoms of hypoglycaemia, but with a measured PG concentration ≤ 3.9 mmol/L (70 mg/dL).
- Documented symptomatic hypoglycaemia: An episode during which typical symptoms of hypoglycaemia are accompanied by a measured PG concentration ≤ 3.9 mmol/L (70 mg/dL).
- Pseudo-hypoglycaemia: An episode during which the person with diabetes reports any of the typical symptoms of hypoglycaemia with a measured PG concentration > 3.9 mmol/L (70 mg/dL) but approaching that level.
- Probable symptomatic hypoglycaemia: An episode during which symptoms of hypoglycaemia are not accompanied by a PG determination but that was presumably caused by a PG concentration ≤ 3.9 mmol/L (70 mg/dL).

Note: Glucose measurements are performed with capillary blood calibrated to plasma equivalent glucose values

Figure 2–2 ADA/ISPAD classification of hypoglycaemia in paediatrics

The following safety endpoints will be assessed:

- Number of treatment emergent hypoglycaemic episodes
 - According to ADA/ISPAD classification
 - According to Novo Nordisk/ISPAD classification
- Number of treatment emergent hypoglycaemic episodes subdivided into daytime and nocturnal (23:00-7:00, both included)
 - According to ADA/ISPAD classification
 - According to Novo Nordisk/ISPAD classification
- Number of treatment emergent meal related (from start of meal until 1, 2, and 4 hours after start of meal and from 1 [exclusive] to 2 hours [inclusive], 2 [exclusive] to 3 hours [inclusive], 3 [exclusive] to 4 hours [inclusive], and from 2 hours [exclusive] to 4 hours [inclusive] after start of meal, respectively) hypoglycaemic episodes
 - According to ADA/ISPAD classification
 - According to Novo Nordisk/ISPAD classification

Data on treatment emergent hypoglycaemic episodes are presented in terms of the number of Subjects with at least one event (N), the percentage of Subjects with at least one event (%), the number of events (E) and the event rate per 100 years of exposure (R). Separate summaries are made by severity (the ISPAD criterion for severe hypoglycaemia⁴) considering all episodes, nocturnal and daytime episodes using Novo Nordisk and ADA classified episodes. Episodes will also be summarised overall and by category in relation to time since start of meal, as occurring within the following time intervals:

- During first 1, 2, and 4 hours after start of meal
- Between 1 (exclusive) to 2 hours (inclusive) after start of meal
- Between 2 (exclusive) to 3 hours (inclusive) after start of meal
- Between 3 (exclusive) to 4 hours (inclusive) after start of meal
- Between 2 hours (exclusive) to 4 hours (inclusive) after start of meal

Non-treatment emergent hypoglycaemic episodes will be listed.

The number of treatment emergent severe or BG confirmed hypoglycaemic episodes (all, daytime, nocturnal) will be analysed using a negative binomial regression model with a log-link function and the logarithm of the time period for which a hypoglycaemic episode is considered treatment emergent as offset. The model will include treatment, region and strata as factors, and will be based on the FAS. To the extent where data allow, separate analyses will be performed for severe episodes (all).

- Number of treatment emergent adverse events (AEs)

AEs will be coded using the Medical Dictionary for Regulatory Activities (MedDRA). AEs will be presented based on system organ class and preferred terms.

A Treatment Emergent Adverse Event (TEAE) is defined as an event that has an onset date on or after the first day of exposure to randomised treatment, and no later than 7 days after the last day of randomised treatment.

TEAEs are summarised descriptively, whereas AE's not defined as treatment emergent are presented in listings, including AEs reported in the 30-day follow-up period. The summaries of TEAEs are made displaying the number of Subjects with at least one event, the percentage of Subjects with at least one event, the number of events and the event rate per 100 Subjects years of exposure. These summaries are done by seriousness, severity, relation to insulin treatment, relation to device, withdrawal due to AEs and outcome.

Furthermore summary tables based on system organ class and preferred term are made for

- All TEAEs
- Serious TEAEs
- Possibly or probably related TEAEs
- Severe TEAEs
- TEAEs with preferred term that are experienced by at least 5% of the Subjects in any treatment arm or by at least 5% of all Subjects

For AEs where additional information is recorded, this will be listed.

AEs occurring during the run-in period are considered non treatment emergent and will be summarised separately.

- Number of treatment emergent injection site reactions

Injection site reactions occurring during the trial, related to either basal and/or bolus insulin will be summarised and listed. No formal statistical analysis will be made.

- Change from baseline in clinical evaluations
 - Physical examination (head, ears, eyes, nose, throat, neck, respiratory system, cardiovascular system, gastrointestinal system incl. mouth, musculoskeletal system, central and peripheral nervous system, skin, Tanner stage)
The physical examination parameters, and their change from baseline, will be summarised descriptively in shift tables. All findings will be listed.
 - Vital signs (blood pressure, pulse)

Vital signs include diastolic blood pressure, systolic blood pressure and pulse. The measurements and their change from baseline will be summarised descriptively.

- Change from baseline in body weight, height, body mass index (BMI) and SD-score of body weight and BMI (z-score)

SD-scores are defined to be able to normalise the body weight in the various age groups. To estimate the growth of children, standardised weight is calculated for each year of age and for each sex. Thus, a child with a weight equal to the mean value for its age and sex has an SD score of 0, while a child with a weight 2 SDs above the mean value for its age and sex has an SD score of +2. The SD scores are derived from the age and sex of the Subjects and the body weight together with growth curves defined for a reference population. SD scores for BMI will be determined in a similar way as SD scores for weight by use of a suitable reference population based on age and sex. For all countries except Japan and India the reference values for the US will be used. The SD scores for Japanese Subjects will be based on country specific references whereas SD scores for Indian Subjects below 5 years of age will be based on World Health Organization (WHO) references and otherwise country specific references.

The measurements and their change from baseline will be summarised descriptively. In addition, the endpoints will be analysed separately using a statistical model using multiple imputation similar to 1) including treatment, region and age group as factors and the corresponding baseline measurement as covariate. The analyses will be based on the SAS and the on treatment observation period.

- Change from baseline in laboratory assessments

- Haematology (haemoglobin, haematocrit, erythrocytes, thrombocytes, and leucocytes)
- Biochemistry (creatinine, , alanine aminotransferase (ALT), aspartate aminotransferase (AST), alkaline phosphatase (AP), sodium, potassium, albumin, and total bilirubin)
- Lipid profile (total cholesterol, high density lipoprotein (HDL), low density lipoproteins (LDL))

Individual laboratory values will be compared to their relevant reference range (when existing) and flagged as being below or above the range. The measurements and their change from baseline will be summarised descriptively. Change from baseline will be summarised descriptively using both the actual values and the low/normal/high categorisation in shift tables.

Lipid endpoints (LDL, HDL, and total cholesterol) will be log-transformed and analysed separately using a statistical model using multiple imputation similar to 1) including treatment, region and strata as factors and the corresponding log-transformed baseline measurement as covariate. The

analyses will be based the FAS and the in trial observation period and repeated using the on treatment observation period. The treatment difference and associated 95% confidence intervals will be back-transformed providing results in terms of ratios of geometric means on the original scale. NovoRapid® will be used as reference.

- Change from baseline in anti-insulin aspart (specific and cross-reacting with human insulin) antibody development

The measurements and their change from baseline will be summarised descriptively. The correlation to other relevant variables such as insulin dose and HbA_{1c} are illustrated using graphs.

3 Changes to the statistical analyses planned in the protocol

Minor editorial corrections have been made throughout the document.

General considerations

As a consequence of the small number of Subjects below 3 years of age included in the trial, the text “Selected tables and figures will also be presented by strata (age).” is changed to Selected tables and figures will also be presented by age group, where age group refers to the following categorisation of age: 1 ≤ age < 6 years, 6 ≤ age < 12 years and 12 ≤ age < 18 years.

Statistical analysis

In the sensitivity analysis 2) for change from baseline in HbA_{1c}, It has been clarified that baseline HbA1c is included in the model as a covariate.

The descriptions of sensitivity analyses have been revised to clarify that all Subjects without a measurement at week 26 (not subjects withdrawing from trial in general) should have their values imputed. The new description is aligned with the primary analysis.

In order to emphasize the difference between sensitivity analyses 3)-b and 3)-c the wording have been rearranged.

The tipping point analyses have been described in more detail and tipping point analysis 5) has been repeated for the in trial observation period in the additional sensitivity analyses 3)-d.

In the statistical analysis for percentage of Subjects reaching HbA_{1c} target, it has been clarified that Subjects without an HbA_{1c} measurement at week 26 will be handled as non-responders for analyses on both the in trial and on treatment observation periods.

In the statistical analysis for percentage of Subjects reaching HbA_{1c} target without severe hypoglycaemia, it has been clarified that Subjects without an HbA_{1c} measurement at week 26 will be handled as non-responders for analyses on both the in trial and on treatment observation periods.

Fluctuation in 8-point

In the analysis of fluctuation of the 8-point self-measured plasma glucose (SMPG) profile “Change from baseline” has been removed. This is done because data are logarithmically transformed and change from baseline potentially include negative values.

CGM endpoints

The percentage of time spent with IG >13.9 mmol/L [250 mg/dL] and incidence of episodes with IG >13.9 mmol/L [250 mg/dL] has been added. Likewise mean, variation, and CV% has been added to further evaluate the effect and safety of fast-acting insulin aspart.

In order to align with previous trials the endpoints IG peak and time to IG peak will be analysed using an analysis of variance model including treatment, region and strata as factors and the corresponding baseline value as covariate. Consequently, the sentence “An additive model will be used to estimate the treatment means and treatment differences with a 95% confidence interval.” has been deleted.

AEs where additional information is recorded

For AEs where additional information is recorded, this will only be listed.

Hypoglycaemic episodes

The endpoints treatment-emergent hypoglycaemic episodes occurring within 1 (exclusive) to 2 hours (inclusive), 2 (exclusive) to 3 hours (inclusive), 3 (exclusive) to 4 hours (inclusive) after start of the meal has been added to further investigate the safety of fast-acting insulin aspart.

Change from baseline in body weight, height, body mass index (BMI) and SD-score of body weight and BMI (z-score)

In order to align with previous trials, analyses of change from baseline in body weight, height, body mass index (BMI) and SD-score of body weight and BMI (z-score) will be based on the safety analysis set and the on treatment observation period.

It has been specified that for all countries except Japan and India the reference values for the US will be used to calculate SD-scores for weight and BMI. The SD scores for Japanese Subjects will be based on country specific references whereas SD scores for Indian Subjects below 5 years of age will be based on WHO references and otherwise country specific references.

Lipid endpoints

In order to align with previous trials, the analyses of lipid endpoints will be based on FAS and the in trial observation period and repeated using the on treatment observation period .

4 References

1. ICH Harmonised Tripartite Guideline. Statistical principles for clinical trials. International Conference on Harmonisation E9 Expert Working Group. *Stat Med*. 1999;18(15):1905-42.
2. Koch GG. Comments on 'Current issues in non-inferiority trials' by Thomas R. Fleming, *Statistics in Medicine*, DOI: 10.1002/sim.2855. *Stat Med*. 2008;27(3):333-42.
